3.4 Safety Endpoints

The following endpoints will be included in the safety analyses:

- Treatment emergent adverse events (TEAEs), serious adverse events (SAEs), AEs leading to discontinuation of the study drug;
- Occurrence of possible glucocorticoid-related AEs;
- Potentially clinically significant laboratory, vital signs, and electrocardiogram (ECG) variables.

4.0 Analysis Populations

The following population sets will be used for the analyses.

ITT Populations

ITT population: The ITT Population includes all subjects who were randomized and received at least 1 dose of study drug.

ITT1 population: The subset of the ITT Population who were randomized and received at least 1 dose of study drug in the Induction Period. The ITT1 Population is the primary analysis population for efficacy analyses of the Induction Period.

ITT2 population: The subset of the ITT population who were randomized and received at least one dose of study drug in the Re-Induction Period. The ITT2 Population is the analysis population for efficacy analyses of the Re-Induction Period.

ITT3 population: The subset of the ITT population who received ABBV-154 for 12 weeks before entering the Maintenance Period (including subjects were randomized to ABBV-154 dose groups in the Induction Period and entered the Maintenance Period from the Induction Period OR were randomized to the placebo group in the Induction Period and entered the Maintenance Period from the Re-Induction Period) AND were randomized and received at least one dose of study drug in the Maintenance Period. The ITT3 Population is the primary analysis population for efficacy analyses of the Maintenance Period.

ITT3-RN population: The subset of the ITT population who were enrolled and received at least one dose of study drug in the randomized portion of the Maintenance Period.

ITT3-NRN population: The subset of the ITT population who were enrolled and received at least one dose of study drug in the non-randomized portion of the Maintenance Period.

ITT3-RES population: The subset of the ITT population who received at least one dose of ABBV-154 rescue therapy in the Maintenance Period.

The ITT Populations (including ITT1, ITT2, ITT3, ITT3-RN, ITT3-NRN populations) will be analyzed as randomized (i.e., according to the randomized/assigned treatment assignment).

Safety Populations

The safety population for the Induction Period (denoted by **SA1**) includes all subjects who received at least one dose of the study drug in the Induction Period.

The safety population for the Re-Induction Period (denoted by **SA2**) includes all subjects who received at least one dose of the study drug in the Re-Induction Period.

The safety population for the Maintenance Period (denoted by **SA3**) includes all subjects who received at least one dose of the study drug in the Maintenance Period.

The all ABBV-154 safety population (**SA-ALL154**) includes all subjects who received at least one dose of ABBV-154 in the Induction Period, or the Re-Induction Period, or the Maintenance Period.

The all ABBV-154 rescue safety population (**SA-RES**) includes all subjects who received at least one dose of ABBV-154 rescue therapy in the Maintenance Period.

The following safety populations are defined for safety analyses based on data from multiple study periods:

SA-IN2: all subjects who received at least one dose of ABBV-154 in both Induction Period and Re-Induction Period.

SA-INMN: all subjects who received at least one dose of ABBV-154 in either Induction Period or Re-Induction Period AND at least one dose of ABBV-154 in the Maintenance Period.

SA-IN2MN: all subjects who received at least one dose of ABBV-154 in the Induction Period AND at least one dose of ABBV-154 in the Re-Induction Period AND at least one dose of ABBV-154 in the Maintenance Period.

For the safety populations, subjects are assigned to a treatment group based on the "as treated" treatment group, regardless of the treatment randomized.

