2.2 Study Design Overview

This is a randomized, double-blind, placebo-controlled Phase 2b study to assess the safety, tolerability, PK, PD, immunogenicity, and efficacy of ABBV-154 in subjects with moderately to severely active CD who had inadequate response to or were intolerant of prior biologics. The enrollment for subjects with prior adalimumab use is capped at approximately 30% of the total enrolled subjects. The study comprises 3 periods: a 12-Week Double-Blind Placebo-Controlled Induction Period, a 12-Week Double-Blind Re-Induction Period (for subjects considered to be clinical non-responders and endoscopic non-responders), and a 40-Week Double-Blind Placebo-Controlled Maintenance Period.

At the Baseline Visit of the Induction Period, approximately 265 subjects will be randomized in a 1:1:1:1 ratio into 4 ABBV-154 treatment groups or placebo:

- Induction Group 1: Loading dose of 150 mg IV at Week 0, followed by 80 mg subcutaneous (SC) at Week 2 and every other week (EOW);
- Induction Group 2: Loading dose of 300 mg IV at Week 0, followed by 230 mg SC at Week 2 and EOW;
- Induction Group 3: Loading dose of 600 mg IV at Week 0, followed by 530 mg SC at Week 2 and EOW;
- Induction Group 4: Loading dose of 600 mg IV at Week 0, followed by 530 mg SC at Weeks 4 and 8, and placebo at Weeks 2, 6, and 10; and

- Induction Group 5: Matching placebo (IV and SC).

At Week 12 of the Induction Period, subjects achieving clinical response, defined as a decrease in Crohn's Disease Activity Index (CDAI) ≥ 100 points from Baseline (CR100) AND/OR endoscopic response defined as a decrease in SES-CD $> 50\%$ from Baseline (or for subjects with isolated ileal disease and a Baseline SES-CD of 4, at least a 2-point reduction from Baseline) (per local read) will receive treatment in the 40-Week Maintenance Period as follows:

- Induction Group 1: Re-randomized in a 1:1 ratio to receive ABBV-154 80 mg SC EOW or matching placebo;
- Induction Groups 2 to 4: Re-randomized in a 1:1:1 ratio to receive ABBV-154 80 mg SC EOW, ABBV-154 230 mg SC EOW, or matching placebo;
- Induction Group 5: ABBV-154 80 mg SC EOW.

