10.0 Safety Analyses

10.1 General Considerations

Safety analyses will be performed on the safety population for the Induction Period (SA1), the Re-Induction Period (SA2), the Maintenance Period (SA3) and SA-RES, SA-ALL154 population as defined in Section 4.0. In addition, safety summaries will be

performed on the safety analysis set for combined data from different periods (SA-IN2, SA-INMN, SA-IN2MN).

The standard safety analyses will include reporting of adverse events (AEs), adverse events of special interest (AESIs), laboratory, and vital signs measurements. Frequency tables and exposure adjusted event rate per 100 patient-years tables of subjects with treatment-emergent adverse events (TEAEs) by system organ class (SOC) and by preferred term (PT) as in the Medical Dictionary for Regulatory Activities (MedDRA) dictionary will be provided by treatment group. All continuous laboratory parameters and vital signs variables at each visit will also be summarized by treatment group. Frequency tables of subjects meeting criteria for potentially clinically important vital sign values and for potentially clinically important laboratory values will be provided by treatment group.

For safety analyses (such as analyses of laboratory and vital signs measurements) in the Induction Period, the baseline value is defined as the last available measurement before study drug administration for all subjects (including subjects who received placebo). For all other safety analyses, the baseline value is defined as the last available measurement before first administration of ABBV-154 for all subjects.

For the safety analysis, subjects are assigned to a treatment group based on the treatment actually received, regardless of the treatment randomized.

Missing safety data will not be imputed.

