10.3 Analysis of Laboratory Data

Data collected from central and local laboratories, including additional laboratory testing due to an SAE, will be used in the analyses. Baseline values collected for SAE-related laboratory assessments on or before the first dose of study drug will be excluded. Data collected more than 70 days after the last dose of study drug of the analysis period (See Section [10.2.1](#)) for the corresponding analysis populations will be excluded.

The clinical laboratory tests defined in the protocol (e.g., hematology and clinical chemistry) will be summarized.

Analysis of Quantitative Laboratory Parameters

Each laboratory variable will be summarized at all time points (starting at baseline) with the number of observations, mean, standard deviation, median, minimum and maximum

for non-missing observations. The change from Baseline at each applicable post-baseline visit will be summarized for selected laboratory variables, with the number of observations, baseline mean, and visit mean. The mean, standard error, and 95% CI will be presented for the change from Baseline for each treatment group.

For each period, treatment group differences for the changes from baseline will be analyzed using a one-way Analysis of Variance (ANOVA) model with treatment as a fixed factor and 95% CI for treatment difference will be presented for selected laboratory parameters.

Shift Table Analyses

Changes in laboratory parameters will be tabulated using shift tables categorized as low, normal, or high based on the normal ranges of the laboratory used for each sample. A shift table summarizes shifts from baseline to minimum and maximum values (based on normal range) will be created. A similar shift table will be provided to summarize shifts from baseline to the final post-baseline value.

Potentially Clinically Significant Laboratory Values

The criteria for potentially clinically significant laboratory values will be determined by CTCAE criteria of Grade 3, Grade 4 and \geq Grade 3, with a grade worsening compared to baseline. Toxicity grading scale is based on National Cancer Institute Common Toxicity Criteria (NCI CTC) AE version 5.0. The number and percentage of subjects meeting the criteria for potentially clinically significant laboratory values will be summarized by treatment group. Listings of subject-level laboratory data will be provided for subjects meeting the criteria.

Assessment of Liver Elevations

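### On SA3 the Maintenance laboratory and vital-sign differences are not randomised comparisons: the 80 mg group includes non-randomised Induction-placebo responders, and the placebo group includes subjects who could not be assigned 230 mg

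*SAP*

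**What the plan says.** SAP 2.2 assigns Week 12 responders to Maintenance by three rules:

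- Responders from the lowest induction dose (Group 1) are randomised again, half to 80 mg and half to placebo.
- Responders from the other three ABBV-154 groups (2 to 4) are split equally between 80 mg, 230 mg and placebo.
- The Induction-placebo responders have a single assignment, with no re-randomisation: "Induction Group 5: ABBV-154 80 mg SC EOW".

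Responders after Re-Induction are also re-randomised.

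For efficacy, SAP 4.0 separates these routes. ITT3-RN holds the randomised portion, and ITT3-NRN holds those who "received at least one dose of study drug in the non-randomized portion of the Maintenance Period". SAP 9.1 limits Maintenance comparisons to the randomised portion and leaves Induction Group 1 direct responders out of 230 mg versus placebo. SAP 13.0 gives the reason: they come from a different randomisation.

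For safety, SAP 4.0 has one Maintenance set, SA3, which "includes all subjects who received at least one dose of the study drug in the Maintenance Period". In the safety sets, "subjects are assigned to a treatment group based on the 'as treated' treatment group, regardless of the treatment randomized". No randomised or non-randomised subset of SA3 is defined. SAP 10.3 then states: "For each period, treatment group differences for the changes from baseline will be analyzed using a one-way Analysis of Variance (ANOVA) model". Treatment is the only factor, and a 95% CI for the difference is given for selected laboratory parameters. SAP 10.4 plans the same for each vital sign. Outside the Induction Period, "the baseline value is defined as the last available measurement before first administration of ABBV-154 for all subjects" (SAP 10.1).

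**The concern.** A between-group difference with a confidence interval is normally read as a randomised contrast. In Maintenance the SAP protects that reading for efficacy but not for safety, although its own reason for the protection applies equally to both.

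Two things set the non-randomised 80 mg subjects apart. They are having their first ABBV-154 exposure, whereas everyone re-randomised has come through an ABBV-154 regimen. They are also measured from a different starting point, so within the 80 mg group the change from baseline at a given visit covers different spans of exposure.

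Safety is part of the primary objective, and Protocol 4.2 says the two maintenance doses were chosen to enable Phase 3 dose selection. The 80 mg, 230 mg and placebo safety results will be read against each other for that purpose.

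**Working it through.** **1. Who can be in each SA3 group.**

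| Route into Maintenance | 80 mg | 230 mg | Placebo | Safety baseline (10.1) |
|---|---|---|---|---|
| Induction Group 1, direct | yes (1:1) | no | yes | Induction Day 1 |
| Induction Groups 2 to 4, direct | yes (1:1:1) | yes | yes | Induction Day 1 |
| ABBV-154 in Induction, via Re-Induction | yes | yes | yes | Induction Day 1 |
| Placebo in Induction, via Re-Induction | yes | yes | yes | Re-Induction Day 1 |
| Placebo in Induction, direct | all, not randomised | no | no | Maintenance entry |

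The last row feeds only the 80 mg group. The first row feeds placebo but never 230 mg. Re-randomisation spreads the Re-Induction rows over all three groups, so their mixed baselines are balanced in expectation. The last row has no counterpart in the other groups.

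**2. The plan's own figures.** The plan gives no number for SA3. Its related figures are the sample sizes in SAP 2.4, for 11% versus 37% at two-sided 0.1. A pooled-variance chi-square calculation gives 94.1% power with 53 per group (stated: more than 90%) and 87.1% with 40 per group (stated: more than 80%). Both reproduce, and this point does not alter them.

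**3. Number of non-randomised subjects.** Entry requires CR100 and/or endoscopic response. SAP 2.4 gives only the placebo endoscopic response rate of 11%, so the entry rate is assumed to lie between 11% and 40%.

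- 53 × 0.11 = 5.8, about 6
- 53 × 0.40 = 21.2, about 21

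**4. Share of the 80 mg group.** With only 40 randomised 80 mg subjects:

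- 6/(40 + 6) = 13%
- 21/(40 + 21) = 34%

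The 40 in SAP 2.4 is a minimum for the Maintenance efficacy analysis. The primary set for that analysis, ITT3, omits subjects who had ABBV-154 in Induction and entered via Re-Induction; SA3 includes them. A fuller flow assumes no dropout and Re-Induction responders split 1:1:1:

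Randomised 80 mg = (Group 1 responders)/2 + (Groups 2 to 4 responders)/3 + (Re-Induction responders)/3

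*Low end (placebo entry 11%, active 37%, Re-Induction 37%)*

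- Re-Induction responders: (212 × 0.63 + 53 × 0.89) × 0.37 = 66.9
- Randomised 80 mg: 19.6/2 + 58.8/3 + 66.9/3 = 51.7
- Share: 5.8/(5.8 + 51.7) = 10%

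*High end (40%, 60%, 40%)*

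- Re-Induction responders: (212 × 0.40 + 53 × 0.60) × 0.40 = 46.6
- Randomised 80 mg: 31.8/2 + 95.4/3 + 46.6/3 = 63.2
- Share: 21.2/(21.2 + 63.2) = 25%

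Across all the rates tried (active 37% to 65%, Re-Induction 37% to 50%) there are 52 to 69 randomised 80 mg subjects, and the share is 10% to 25%.

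**5. Effect on the estimate.** If the mean change in the non-randomised subjects differs by δ from that in the randomised 80 mg subjects, the 80 mg mean, and so the 80 mg minus placebo difference, moves by share × δ. That is 0.10δ to 0.25δ, or 0.34δ at most. The sign of δ is unknown.

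**6. The 230 mg versus placebo comparison.** The randomised placebo group is the same size as the randomised 80 mg group. The Group 1 share of placebo is (19.6/2)/51.7 = 19% at the low end and (31.8/2)/63.2 = 25% at the high end. None of these subjects has a counterpart on 230 mg.

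**The case against.** The strongest defence is that pooling everyone dosed, by treatment received, is ordinary practice for safety. Protocol 7.7 promises summaries only, and there is no type I error control to protect. For description this is right, and SA3 should stay. It does not cover 10.3 and 10.4, which add estimated differences with intervals.

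The SAP does not lay out the SA3 table columns, and table shells might separate the groups. The single 80 mg group is an inference from the as-treated rule and the lack of any split. Nothing in the SAP requires a split, though, so it should be written down.

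SA-INMN already requires ABBV-154 before and during Maintenance, which excludes the direct Induction-placebo entrants. But it has no randomised placebo comparison and it counts events from before Maintenance, so it does not replace the missing contrast.

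A reader might infer more than the documents support:

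- *That the adverse event comparisons are invalid.* SAP 10.2 plans frequencies and exposure-adjusted rates by group, with no difference, interval or test. What remains is that reading the columns side by side mixes first-exposure and pre-exposed subjects in 80 mg.
- *That 80 mg must look worse than 230 mg.* First exposure falls only in the 80 mg group, but hypersensitivity and infection can occur in any group. The naive subjects also have less cumulative exposure, which could work the other way.
- *That every re-randomised subject has an Induction Day 1 baseline.* Induction-placebo subjects who enter via Re-Induction have theirs at Re-Induction Day 1.
- *That a third of the 80 mg group is non-randomised.* That needs only 40 randomised 80 mg subjects together with the highest assumed entry rate.

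**Conclusion.** The point holds for the planned Maintenance differences in selected laboratory parameters and in vital signs. On SA3 the 80 mg comparisons include a non-randomised, ABBV-154-naive component with a later baseline. The 230 mg versus placebo comparison has a separate fault from the Group 1 responders in the placebo group. For adverse events it is a matter of display, because no contrast is planned.

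The non-randomised part is about 6 to 21 subjects, roughly 10% to 25% of the 80 mg group, and up to 34% if only 40 subjects are randomised to 80 mg. This rests on assumed entry and response rates, no dropout, and a 1:1:1 split after Re-Induction. The direction of bias is not established. The primary endpoint, the Maintenance efficacy comparisons and the stated power are unaffected. The change should be made, since it is cheap and follows a principle the SAP already applies to efficacy.

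**What to change.** In the SAP:

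1. Keep SA3 for overall description of Maintenance safety.
2. Define SA3-RN (re-randomised) and SA3-NRN (not re-randomised) in 4.0, mirroring ITT3-RN and ITT3-NRN, and show the non-randomised 80 mg subjects in their own column in the Maintenance safety tables.
3. State in 10.3 and 10.4 that Maintenance treatment differences are computed on SA3-RN.
4. Apply the 9.1 exclusion of Induction Group 1 direct responders to 230 mg versus placebo.

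Steps 3 and 4 leave a 1:1 allocation within each entry route for both active-versus-placebo comparisons (taking 1:1:1 after Re-Induction), so the one-way ANOVA can stay as planned.

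The cost is SAP wording and one table column, with no new data. The 80 mg group in these differences loses the 6 to 21 non-randomised subjects, and the placebo group used against 230 mg loses its Group 1 direct responders, so those intervals will be somewhat wider.

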5.5 Withdrawal of Subjects and Discontinuation of Study

AbbVie may terminate this study prematurely at any time, either in its entirety or partially (discontinue one or more treatment groups) or at any site. The study may be discontinued or terminated in case of an unacceptable risk, any relevant toxicity, or a negative change in the risk/benefit assessment. This might include the occurrence of AEs with a character, severity or frequency that is new in comparison to the existing risk profile. In addition, data derived from other clinical trials or toxicological studies which negatively influence the benefit-risk assessment might cause discontinuation or termination of the study. The investigator may also stop the study at his/her site if he/she has safety concerns. If AbbVie terminates the study for safety reasons, AbbVie will promptly notify the investigator. Advance notice is not required by either party if the study is stopped due to safety concerns.

A subject may voluntarily withdraw from the study at any time for any reason. An investigator may discontinue a subject's participation at any time for any reason. The AbbVie TA MD may mandate individual subject discontinuation from study drug in case of a safety concern.

Subjects must have study drug discontinued immediately if any of the following occur:

- Abnormal laboratory result or AE that meets the criteria for discontinuation of study drug as stated in Section 6.2, or rule out safe continuation of the study drug, as determined by the investigator or the AbbVie TA MD.
- Serious infection (e.g., sepsis) that cannot be adequately controlled within 2 weeks by anti-infective treatment or would put the subject at risk with continuation of study drug.
- Subject is noncompliant with TB prophylaxis (if applicable) or develops active TB at any time during the study.
- Malignancy or high-grade dysplasia of the gastrointestinal tract, except for localized NMSC or carcinoma in-situ of the cervix.
- The subject develops an anaphylactic reaction or anaphylactic shock.
- The investigator believes it is in the best interest of the subject.
- The subject requests withdrawal from study drug or the study.
- Eligibility criteria violation was noted after the subject started study drug and continuation of the study drug would place the subject at risk.
- Introduction of prohibited medications or dosages and continuation of the study drug would place the subject at risk.

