10.2.1 Treatment-Emergent Adverse Events

Induction Period (SA1 population): TEAEs for the Induction Period are defined as events that begin either on or after the first dose of the study drug in the Induction Period and until (i) the first dose of study drug in the Re-Induction Period (if applicable), or (ii) until first dose of study drug in the Maintenance Period (if applicable), or (iii) within 70 days after the last dose administration of the study drug in the Induction Period, whichever is earlier.

Re-Induction Period (SA2 population): TEAEs for the Re-Induction Period are defined as events that begin either on or after the first dose of the study drug in the Re-Induction Period and until (i) first dose of study drug in the Maintenance Period (if applicable), or (ii) within 70 days after the last dose administration of the study drug in the Re-Induction Period, whichever is earlier.

Maintenance Period (SA3 population): TEAEs for the Maintenance Period are defined as events that begin either on or after the first dose of the study drug in the Maintenance Period and until (i) within 70 days after the last dose administration of the blinded study drug in the Maintenance Period, or (ii) initiation of ABBV-154 rescue therapy, whichever is earlier.

ABBV-154 Rescue Therapy (SA-RES population): TEAEs for the ABBV-154 rescue therapy are defined as events that begin either on or after the first dose of the ABBV-154 rescue therapy in the Maintenance Period and until 70 days after the last dose administration of the study drug in the Maintenance Period.

All ABBV-154 (SA-ALL154 population): TEAEs for "All ABBV-154" are defined as events that begin either on or after the first dose of ABBV-154 and within 70 days after the last dose of ABBV-154 in the study. Events that begin when subjects on Placebo will be not included.

Safety analyses from combined periods:

Induction Period + Re-Induction Period ABBV-154 (SA-IN2 population): TEAEs for "Induction Period + Re-Induction Period ABBV-154" (SA_IN2) are defined as events that begin either on or after the first dose of ABBV-154 in the Induction Period and until (i) first dose of study drug in the Maintenance Period (if applicable), or (ii) within 70 days after the last dose of study drug in the study, whichever is earlier.

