10.2.4 Treatment-Emergent Adverse Events per Patient-Years of Exposure

TEAEs will be summarized by event rate per 100 subject years, defined as

$$100 \times \frac{\text{Number of TEAEs}}{\text{Total Patient Years}}$$

where total patient years is defined as the sum of the study drug exposure of all subjects, normalized by 365.25, and rounded to 1 decimal place. Note that one event per preferred term per day per subject will be counted in the calculation of the number of AEs (i.e., a preferred term will not be counted twice on the same day for the same subject).

The TEAE rates per 100 patient-years of exposure will be provided for each AE category in the AE overview summary (defined in Section 10.2.2) and for TEAE summary by SOC and PT.

The study drug exposure for each safety population is defined as last dose date plus 70 days, minus the first dose date. For SA-All154 safety population, the duration when subjects on Placebo will not be included in the calculation.

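### SA-IN2, SA-INMN and SA-IN2MN require a later-period ABBV-154 dose but start the clock at the first one, so their rates of death and dosing-ending events are biased downward

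*SAP*

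**What the plan says.** **Membership (SAP 4.0).** SA-IN2 is "all subjects who received at least one dose of ABBV-154 in both Induction Period and Re-Induction Period". SA-INMN needs a dose "in either Induction Period or Re-Induction Period AND at least one dose of ABBV-154 in the Maintenance Period". SA-IN2MN needs an Induction dose "AND at least one dose of ABBV-154 in the Re-Induction Period AND at least one dose of ABBV-154 in the Maintenance Period".

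**Event window (SAP 10.2.1).** For SA-IN2 and SA-IN2MN, TEAEs are "events that begin either on or after the first dose of ABBV-154 in the Induction Period and until" a later cut-off. For SA-INMN the window opens at the first ABBV-154 dose in Induction or Re-Induction, so a member who had placebo in Induction starts at Re-Induction. The SA-IN2 window closes at the first Maintenance dose, if there is one. The windows of the other two sets close at ABBV-154 rescue, if it is given.

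**Exposure (SAP 10.2.4).** "The study drug exposure for each safety population is defined as last dose date plus 70 days, minus the first dose date". No start date is given for each combined set; the first ABBV-154 dose of the window is the natural reading.

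**Use.** SAP 10.1 adds to the main safety analyses summaries "performed on the safety analysis set for combined data from different periods (SA-IN2, SA-INMN, SA-IN2MN"). The overview in SAP 10.2.2 includes deaths, TEAEs leading to discontinuation and AESIs; TEAE categories are given as percentages and per 100 patient-years.

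**Stopping rules (Protocol 5.5).** Study drug must be stopped at once for several events. One is "The subject develops an anaphylactic reaction or anaphylactic shock"; others are active TB and malignancy, with named exceptions. SAP Appendix G lists serious allergic reactions, active TB and malignancies as AESIs.

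**The concern.** Whether a subject belongs to one of these sets is settled by a future dose, but events and time are counted from a past one. This is immortal time. A subject who dies in Induction, or stops drug for good then because of anaphylaxis, never receives the qualifying dose and is in none of the three sets. Those who do qualify bring 12 or 24 earlier weeks into the denominator, and in that time they cannot have had an event that ended dosing before the qualifying dose.

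The bias favours the drug. A reader who sets SA-IN2MN beside SA-ALL154 could see fewer discontinuations or anaphylactic reactions per 100 patient-years and conclude that longer exposure is better tolerated, when part of the difference comes from the set definition.

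**Working it through.** The plan states no harm rate that this point turns on, so there is no figure of its own to reproduce.

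**Inputs.** Induction and Re-Induction last 12 weeks (84 days) each, with the last dose at Week 10 (day 70) of the period. The last Maintenance dose is at Week 38 (day 266 of Maintenance). Exposure runs to 70 days after the last dose (SAP 10.2.4).

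**Step 1: guaranteed share of exposure, for a completer without rescue.** Share = days from first ABBV-154 dose to qualifying dose ÷ (last dose + 70 − first dose).

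- SA-IN2: qualifies on day 84; last dose 84 + 70 = 154; exposure 154 + 70 = 224. Share 84/224 = 37.5%. For a member who goes on to Maintenance, the event window closes at day 168, and 84/168 = 50% of it is guaranteed.
- SA-INMN after one active 12-week period: qualifies on day 84; last dose 84 + 266 = 350; exposure 420. Share 84/420 = 20%. A member on placebo in Induction gives the same result, because the clock starts at Re-Induction.
- SA-INMN after two active periods, and SA-IN2MN: qualifies on day 168; last dose 168 + 266 = 434; exposure 504. Share 168/504 = 33%.

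**Step 2: from share to bias.** Suppose an event is rare, has constant hazard over the whole window and always ends dosing. The reported rate is then about the true rate times (1 − share). An event that consists of stopping drug cannot fall in the 70 days after the last dose, so for it the relevant share is larger: 84/154 = 54.5% (SA-IN2), 84/350 = 24% (SA-INMN, one period) and 168/434 = 38.7% (SA-IN2MN, and SA-INMN after two).

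**Step 3: simulation of a dosing-ending event.** 2,000,000 subjects start ABBV-154 in Induction, under the SAP's entry and exposure rules. These assumptions are not in the documents: hazard 20 per 100 patient-years on drug, either constant or tripled in the first 84 days; 50% response per 12-week period; two thirds of responders on active drug in Maintenance; no other dropout and no rescue. SA-IN2 exposure runs to 70 days after the last Re-Induction dose. The comparator is the same planned paths without the requirement to reach the later period. Entries are rates per 100 patient-years.

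| Set | Constant: as defined / comparator | Ratio | Tripled early: as defined / comparator | Ratio |
|---|---|---|---|---|
| SA-IN2 | 6.18 / 13.61 | 0.45 | 6.14 / 28.41 | 0.22 |
| SA-INMN | 11.56 / 16.64 | 0.69 | 11.59 / 24.64 | 0.47 |
| SA-IN2MN | 10.21 / 17.02 | 0.60 | 10.14 / 24.11 | 0.42 |

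At constant hazards of 10 and 40 per 100 patient-years the ratios hardly change: about 0.45, 0.69 to 0.70 and 0.59 to 0.60. The early tripling is almost invisible in the three sets as defined, whereas SA-ALL154 rises from 15.41 to 25.91.

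**Step 4: clock started at the qualifying dose.** With constant hazard 20, the rates become 9.93 (SA-IN2), 15.62 (SA-INMN) and 15.63 (SA-IN2MN), against 15.41 in SA-ALL154. SA-IN2 stays lower mainly because the 70-day tail is a large part of its short window.

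**The case against.** The strongest reply is that nothing is lost. SAP 10.1 names SA1, SA2, SA3, SA-RES and SA-ALL154 first; the combined sets are an addition. SA1 keeps everyone who stops in Induction. SA-ALL154 has no later-dose condition. SA2 and SA3 open their windows at the dose that defines membership. SAP 5.0 reports discontinuations by reason for each period, and SAP 10.2.5 tabulates and lists SAEs, deaths and adverse events leading to discontinuation. All of this stands and limits the point to three supplementary sets, but it does not correct the tables produced for them.

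Second, the sets describe treatment paths. SA-IN2 leaves out Week 12 responders by design, and many responders are absent from the Maintenance sets because they were re-randomized to placebo. So not every exclusion is a failure to stay on drug. That is true, but those who stopped for harm are still removed as well.

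Third, restarting every event at the qualifying dose would nearly duplicate SA2 and SA3. It would also discard early-onset events in subjects who continued, which are the multi-period data that these sets combine. This also stands, and the fix is limited accordingly.

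A reader might infer that discontinuations with onset in the guaranteed time are zero by definition, or that all AESIs are affected. The documents do not support either. TEAEs are assigned by onset, so an event that begins in Induction and stops drug only after the qualifying dose is counted. So are events after which dosing continued or restarted: Protocol 6.2 allows restart after a treated serious infection and sets no mandatory stop for adrenal insufficiency.

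**Conclusion.** In SA-IN2, SA-INMN and SA-IN2MN, percentages and rates per 100 patient-years for deaths and for adverse events that end dosing before the qualifying dose are biased downward. The direction follows from the definitions. For the rates, it rests on reading the first dose date in SAP 10.2.4 as the first ABBV-154 dose of the combined window.

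The firm figures are the guaranteed shares for completers without rescue: 37.5% (SA-IN2), 20% or 33% (SA-INMN, after one or two active periods) and 33% (SA-IN2MN). It would be tempting to read them as the size of the bias. They equal it only for a rare event with constant hazard through the 70-day tail that always ends dosing. Under the simulation's assumptions the shortfall for discontinuations is larger: about 55%, 30% and 40% with constant hazard, and more if harm comes early.

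The documents do not support the wider inference that serious harms disappear from the report or that the Induction comparison with placebo is distorted. SA1, SA2, SA3 and SA-ALL154 are not affected.

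**What to change.** In SAP 10.2.2 and 10.2.4, report deaths, TEAEs leading to discontinuation and rates of AESIs that require stopping drug only from SA-ALL154 and the period sets SA1, SA2 and SA3. Take whole-course rates of these outcomes from SA-ALL154.

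If these rows are also shown for the combined sets, count both events and exposure from the qualifying dose: the first ABBV-154 dose in Re-Induction for SA-IN2, and the first blinded ABBV-154 dose in Maintenance for SA-INMN and SA-IN2MN. A subject whose only ABBV-154 in Maintenance is rescue then adds no time to these rows, in line with the rescue cut-off in 10.2.1.

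Keep the combined sets for all other TEAEs, with a label that they are conditional on reaching the later period. State the exposure start date for each set in 10.2.4.

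The cost is SAP wording and table programming, with no new data. The downside is that the combined-set tables carry fewer rows or fewer events.
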